5.1. Intent-to-Treat (ITT) Analysis

OLS regression models will estimate the average treatment effect of assignment to the treatment group on changes in each outcome.

Models:

1. Bivariate association between treatment assignment and outcome change.

2. Model 1 + controls for baseline value of outcome.
3. Model 2 + controls for baseline covariates associated with outcome of interest at baseline.

5.2. Instrumental Variable (IV) Analysis

Participants are considered to have adhered to the intervention if they received both a completion certificate and seed capital.

Two-stage least squares (2SLS) using `ivregress 2sls` in Stata.

Stage 1: Predict adherence using treatment assignment as an instrument.

Stage 2: Estimate the causal effect of adherence on outcome changes.

6. Handling Attrition

- Attrition Analysis: Logistic regression will assess whether loss to follow-up is associated with baseline characteristics.

7. Sensitivity Analyses

Compare results using:

- Change scores vs. endline-only models controlling for baseline values.

8. Software

All analyses will be conducted in Stata (version 16), using appropriate packages for regression, 2SLS, and multiple imputation.

9. Ethical Considerations

All study protocols and procedures were approved by the Washington University in St. Louis IRB (Approval #202407174).

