- Baseline Balance: Descriptive statistics will be computed separately by study arm. Mean comparisons will be conducted using independent samples t-tests.
- Imbalance Adjustment: Outcomes found to differ significantly at baseline between groups will be included as controls in regression models of change scores.

5. Estimating Treatment Effects

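### SAP 5.2 names no baseline value in either 2SLS stage, so the main LATE is less precise than it could be and pairs only with the unadjusted ITT model (minor, free to improve)

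*SAP*

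**What the plan says.** The LATE is a stated objective in SAP section 1. SAP 5.2 sets out its estimation in three lines: "Two-stage least squares (2SLS) using `ivregress 2sls` in Stata", then "Stage 1: Predict adherence using treatment assignment as an instrument", then "Stage 2: Estimate the causal effect of adherence on outcome changes". Adherence is binary: "Participants are considered to have adhered to the intervention if they received both a completion certificate and seed capital". No baseline value or covariate is named, and there is no reference back to the models of 5.1.

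SAP 5.1, by contrast, lists its adjustment sets. Model 1 is the "Bivariate association between treatment assignment and outcome change". Model 2 is "Model 1 + controls for baseline value of outcome". Model 3 adds baseline covariates. None of the three is named as primary.

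Two other places bear on the point. SAP section 4 says: "Outcomes found to differ significantly at baseline between groups will be included as controls in regression models of change scores". SAP section 7 plans a comparison of "Change scores vs. endline-only models controlling for baseline values". Neither says whether it covers the 2SLS models.

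**The concern.** With one instrument, one endogenous variable and no covariates, 2SLS on the change score reproduces ITT Model 1 rescaled by the adherence difference. A raw change score subtracts the whole baseline value, whereas regression adjustment subtracts only the part that predicts the endline value. The raw version is therefore noisier whenever the baseline-to-endline correlation is below 1.

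Two things are at stake. The interval for the LATE is wider than the data require. And the LATE can differ from the Model 2 ITT, including in its significance verdict, because the two handle a chance baseline difference differently. A reader who sets Model 2 beside the LATE could put that difference down to adherence.

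**Working it through.** **Inputs from the protocol (sample size section).** d = 0.5, 80% power, one-sided alpha 0.05, 63 analysable girls per arm, 90 per arm enrolled.

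**Assumed, because the documents give no figure.** Baseline-to-endline correlation r of 0.3 to 0.8; equal SDs at both times; adherence of 50% to 90% (70% as the central case); no adherence in the control arm; in the simulation, adherence unrelated to the girl's outcome.

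**The plan's own figure.** n per arm = 2(z_alpha + z_power)²/d². Two-sided 0.05: 2(1.960 + 0.842)²/0.25 = 62.8, so 63. One-sided 0.05: 2(1.645 + 0.842)²/0.25 = 49.5, so 50. Inflation: 63/(1 − 0.30) = 90. The 63 thus reproduces as a two-sided calculation although the text says one-sided, so power is shown both ways below.

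**Step 1: what 5.2 estimates.** LATE = (ITT effect)/(difference in adherence). At 70% adherence an ITT effect of 0.5 SD is a LATE of 0.5/0.7 = 0.71 SD.

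**Step 2: precision.** In SD² units the variance of the arm difference is (2/63) × 2(1 − r) for the raw change score and (2/63) × (1 − r²) with baseline adjustment. The ratio is 2/(1 + r), whatever the sample size. The equivalent loss of sample is (1 − r)/2.

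| r | SE, raw change | SE, adjusted | SE ratio | Equivalent loss of girls |
|---|---|---|---|---|
| 0.3 | 0.211 | 0.170 | 1.240 | 35% |
| 0.5 | 0.178 | 0.154 | 1.155 | 25% |
| 0.7 | 0.138 | 0.127 | 1.085 | 15% |
| 0.8 | 0.113 | 0.107 | 1.054 | 10% |

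These SEs are on the ITT scale; dividing by the adherence difference gives the LATE scale. A simulation of 4,000 trials at 63 per arm and 70% adherence gave LATE SD ratios of 1.23, 1.15 and 1.09 for r = 0.3, 0.5 and 0.7. At 50% and 90% adherence they ran from 1.07 to 1.23. The mean estimates, with and without baseline, were within 0.01 of the true LATE in every setting.

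**Step 3: power of the LATE test, without and with baseline.**

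| r | Two-sided 0.05 (simulated, 70% adherence) | One-sided 0.05 (normal approximation) |
|---|---|---|
| 0.3 | 67% → 83% | 77% → 90% |
| 0.5 | 79% → 88% | 88% → 94% |
| 0.7 | 94% → 97% | 98% → 99% |

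The one-sided column uses the step 2 SEs; in that approximation the adherence rate cancels.

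**Step 4: agreement with ITT Model 2.** Models 1 and 2 differ by (1 − r) × (baseline difference between arms). At 63 per arm the baseline difference has SD √(2/63) = 0.178, so the gap has SD 0.125, 0.089 and 0.053 for r = 0.3, 0.5 and 0.7. As an example, a baseline difference of 0.2 SD at 70% adherence moves the LATE by 0.2(1 − r)/0.7 = 0.20, 0.14 and 0.09 SD. The simulated unadjusted LATE has SD 0.30, 0.26 and 0.20, so the shift is about 0.7, 0.5 and 0.4 of a standard error.

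**Step 5: how far the section 4 rule helps.** A t-test at 63 per arm is significant at a difference of about 1.98 × 0.178 = 0.35 SD, which happens by chance in about 5% of comparisons. Below that, an unadjusted gap of up to (1 − r) × 0.353 = 0.25, 0.18 and 0.11 SD remains on the ITT scale. Simulated results at 70% adherence:

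| r | Verdicts differ from Model 2: no baseline | Section 4 rule applied | Baseline in both stages |
|---|---|---|---|
| 0.3 | 20% | 18% | 2% |
| 0.5 | 12% | 11% | 1% |
| 0.7 | 3% | 3% | 1% |

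With the section 4 rule, two-sided power is 68%, 80% and 94%, barely above the unadjusted figures.

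**The case against.** The strongest reply is that silence is not exclusion. The lines in 5.2 identify the instrument, the endogenous variable and the outcome; they do not say that covariates are left out. That stands, and a reader should not infer that the SAP forbids a baseline term. But 5.1 spells out its covariates and 5.2 names none, so the literal specification is the unadjusted one.

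Section 4 can fairly be read to reach a 2SLS on change scores, and it addresses chance imbalance directly. It acts only on significant imbalance, though, and step 5 shows that it recovers little. Section 7 may also reach the IV analysis, but only as a sensitivity comparison, which leaves the main LATE as it is.

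It is also true that the LATE as written matches Model 1, which is itself a planned model, and that the SAP names no ITT model as primary. One might infer that the LATE conflicts with the trial's main ITT analysis. The documents do not support that: the mismatch is with Models 2 and 3 only. Nor is the difference beyond untangling. Models 1 and 2 will both be reported, and their gap divided by the adherence difference gives the shift in the LATE, up to the small change that adjustment makes to the adherence difference.

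Finally, at the stated one-sided 0.05 and r of 0.5 or more, the unadjusted analysis already has more than 80% power under these assumptions.

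**Conclusion.** The point holds as a minor one. As written, the main LATE lacks a baseline term, has no counterpart to ITT Models 2 and 3, and carries a standard error about 24%, 15% or 8% too large at r = 0.3, 0.5 or 0.7 (about 5% at 0.8). It is tempting to call the LATE biased by baseline imbalance. It is not: under randomisation both versions are unbiased, and the shifts in step 4 are chance variation that the wider interval already reflects.

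The size rests on r, equal SDs and the adherence rate, none of which the documents give. It applies to the continuous outcomes, such as the RCADS-25 score, and not to the 12 dichotomous DSM domains. That the adjusted version is more precise holds, given equal SDs, for any r below 1.

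**What to change.** In SAP 5.2, state that the baseline value of the outcome enters both 2SLS stages as an exogenous covariate: `ivregress 2sls change baseline (adherence = assignment)`. State that this main LATE pairs with ITT Model 2 on the same analysis set. Add a sentence saying whether sections 4 and 7 apply to the IV models. Once baseline is in the model, using the endline score in place of the change score gives the same adherence coefficient, so a section 7 comparison for the IV would amount to the unadjusted against the adjusted version.

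The cost is a line or two of SAP text and one extra term in the command. No new data are needed: baseline is already collected, and a change score cannot be computed without it.
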